## 19. Potential Benefits to Subjects

The patients enrolled are already opting for third line, non-surgical treatment of their OAB. Participation in this study may help to improve an individual participant's condition, but it is also possible that the condition may not improve. There is no guarantee that any individual will personally benefit by participating in this research study. Women randomized to TENS

PROTOCOL TITLE: INTENSE: INvestigation of TENS Efficacy versus Posterior Tibial Nerve Stimulation for overactive bladder

will potentially get benefit from having a personal device they can keep and use on their own time. Women randomized to TENS will not require weekly in-person office visits, which will save time on travel, office visits, and potential COVID-19 or other viral exposures as compared to the PTNS group. Participation in this study may provide information that may help other people who have a similar medical problem in the future. The literature supports improvement of QOL with improved OAB symptoms. PTNS and TENS have both been successfully used to treat OAB and UUI in the past.

## **20. Recruitment Methods**

The Urogynecology clinics at UNM Eubank, and SRMC have a large referral population of patients with pelvic floor conditions such as OAB. Subjects will be identified in the clinics at UNM Eubank clinic and SRMC by investigators when they present either in person or virtually (telephone or Zoom visits) for visits for OAB care. The patients will be counseled about possible treatment options for OAB and they will be introduced to the study and provided with written information that may help them decide if participation in the study is right for them. Subjects are encouraged to consult with family, friends, and primary health care providers, as well as communicate any questions they may have before beginning the consent process. We will request a waiver of HIPAA authorization for recruitment purposes.

If a woman declines to participate or is withdrawn from the study either by her desire or that of the research staff, she will be offered the same treatment options. Her follow up appointments will be the same regardless of participation in the study.

Potential participants may also self-identify through a recruitment material flyer that will be placed in Eubank clinic restrooms, waiting area and in the OB/GYN department at UNM. The proposed recruitment flyer is uploaded in the supplemental materials section.

## **21. Provisions to Protect the Privacy Interests of Subjects**

Privacy concerns are considered with every patient seen at the UNM and SRMC clinics. Participants approached and/or interviewed in the clinic setting will be in either private offices or examination rooms in the clinics, personal Zoom or on telephone calls that are HIPAA compliant. All staff, including research staff, are well-versed in sensitive health care discussions and procedures. Telephone interviews for recruitment and study data gathering are conducted in the research staff area or private physician offices, where all staff have received CITI Training. The office area designated for the entire Urogynecology research staff is isolated from the clinical administrative staff area, providing protection for participants and potential participants during screening, recruitment, study-designated calls, and data entry. All study sheets used to collect patient information will be de-identified.

At all times throughout the clinical investigation, confidentiality will be observed by all parties involved. All data will be secured against unauthorized access. Privacy and confidentiality of information about each subject will be preserved in study reports and in any publication. Each subject participating in this study will be assigned a unique identifier. An IRB-approved HIPAA authorization within the consent is required to be given to the

PROTOCOL TITLE: INTENSE: INvestigation of TENS Efficacy versus Posterior Tibial Nerve Stimulation for overactive bladder

patient. All documents containing personal health information (screening logs, consent documents, data forms) are maintained in locked cabinets with access available only to research staff and investigators. Data is entered into a password protected system. No individual identifiers, other than email to send consent and questionnaire forms, are entered into the system. The sole link with personal information is maintained by the research team on a password protected computer on a secure UNM OBGYN department server with access limited to authorized research staff and investigators. This information is only to be used at the study center.

**22. Economic Burden to Subjects**

The cost of the TENS 7000 device and associated materials will be the responsibility of the subject if randomized to the TENS group. If funds become available, we will plan to compensate participants in both the PTNS and TENS arms with a \$50 merchandise card. Participants will not be billed for any other study materials.

Participants have already chosen to undergo third line, non-surgical treatment of their OAB/UII and will receive prior authorization from their third-party payers if randomized to PTNS or will have worked out financial assistance if needed. These costs will be billed to their insurance provided and costs may range from copay only to full cost of treatment.

Research Procedures	Number of Samples/Procedures	Responsible Party	
		Study	3 rd Party Payer or Participant
TENS Device	1		
_____	_____		
Standard of Care Procedures	Number of Samples/Procedures	Responsible Party	
		Study	3 rd Party Payer or Participant
PTNS Treatment	12		
Clinic visit	1-2		
Transportation to PTNS treatment	0-12		
Transportation to Clinic Visits	1-2		
Phone Visit – remote	2		
_____	_____		
_____	_____		
_____	_____		

**23. Compensation**

At this time, no compensation will be provided to study participants. If funds become available, each participant will be compensated with a merchandise cards worth \$50: a \$25 merchandise card when they complete 6 weeks of treatment (6 weekly sessions in the case of the PTNS group) and another \$25 merchandise card when they complete 12 weeks of treatment (12 weekly sessions in the case of the PTNS group). These compensations will be

PROTOCOL TITLE: INTENSE: INvestigation of TENS Efficacy versus Posterior Tibial Nerve Stimulation for overactive bladder

provided to patients when they complete 6 sessions or 12 sessions and the resulting outcomes measures, regardless of when they complete them. So, for example, if a PTNS patient does 6 sessions of PTNS in an 8-week period, they will get the \$25 merchandise card when they complete the 6 sessions (after 8 weeks). A modification will also be submitted to the IRB to update the protocol and consent with compensation amounts. This payment will be reasonable compensation for the purchase of a TENS device and the inconvenience of participating in a research study due to the additional time the study questionnaires will require from the participant.

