- The patient sits in a reclining chair, with their legs elevated on a foot rest. The area for needle placement is cleaned with an alcohol swab. A 34 gauge needle is inserted percutaneously approximately 5 cm cephalad to the medial malleolus of the right or left ankle (patient's choice) at a 60 degree angle. A surface electrode is placed on the medial aspect of the ipsilateral calcaneus. The needle and electrode are connected to a low voltage (9V) electrical stimulator (brand name). Stimulation current with a fixed frequency of 20 Hz and a pulse width of 200  $\mu$ sec is increased until flexion of the big toe or fanning of all toes visualized, or until the woman reports a tingling sensation across the heel or sole of the foot. The current is then set to the highest level of tolerable to the patient (0-10 mA) and then she undergoes therapy for 30 minutes. If no response is seen (no fanning of toes or flexion of big toe or no report of a tingling sensation across the heel or bottom of the foot), the needle is replaced on the same or opposite side until the appropriate response is seen. The needle placement sites will be monitored for bleeding, bruising, irritation or a hematoma. This will be repeated each week, until the completion of 12 weeks of treatment.
- If women assigned to the PTNS arm miss one of their weekly office PTNS sessions, they will be permitted to "make up" the missed session at the end of the 12 weeks, and their "12 week" outcome measures will be performed following that last session (13 weeks following randomization). Women that have missed this one session and made up the session at the end of the treatment course will be considered "fully compliant" with treatment and analyzed in the "per protocol" analysis as having completed the PTNS treatment course per protocol.
- If women assigned to the PTNS arm miss more than one of their weekly office PTNS sessions, they will not be allowed to make up the extra sessions and their

PROTOCOL TITLE: INTENSE: INvestigation of TENS Efficacy versus Posterior Tibial Nerve Stimulation for overactive bladder

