participation in the study or outcome measurement will not be extended further than 13 weeks after randomization. However, they will not be withdrawn from the study for missing sessions, and will be followed for outcomes and adverse events despite missing sessions of PTNS. Women that miss more than one session of PTNS or miss one session and do not make it up at the end will be considered “not fully compliant” with PTNS treatment, and will be analyzed in the “intention-to-treat” analysis in the PTNS arm but not in the “per protocol” analysis in the PTNS arm.

Prior to their week 6 session, women will be asked to complete a 3-day voiding diary in the three days before their scheduled PTNS treatment and bring it to clinic. At their week 6 session, women will complete the UDI and PSQ questionnaires via REDCAP on an iPad in clinic. The same will be conducted for their week 12 session. Patient compliance of attending PTNS sessions will be recorded.

**12.1.2. TENS:** Women randomized to the TENS groups will begin therapy after their baseline evaluation is complete. They will be asked to purchase a TENS 7000 device (estimated cost \$30) and will administer self-treatment at home, daily for 20 minutes, for 12 weeks total. Current practice in the Urogynecology clinic is to offer TENS therapy to women as an alternative to in-person maintenance therapy for after completing PTNS 12 sessions. TENS 7000 device is off label for its use in the treatment of OAB. If funding is secured, women in both PTNS and TENS group will be reimbursed with a merchandise card. Participants will be asked to bring their device to clinic to ensure the correct device is used, standardize settings and provide the following patient education:

- Proper TENS device set up and pre-set standardized settings, detailed below
- Proper electrode pad placement that will be demonstrated. Electrodes will be traced with a skin marker during this clinic visit and pictures will be provided to ensure correct placement at home. If the patient has a camera, they can photograph electrode placement while in clinic.
- Determine intensity level
- Patients will be notified that they can go about their regular daily activities with the TENS device in place, so that treatment does not interfere with normal work or household duties. However, they will be instructed to not use the device while exercising due to sweat causing reduced adhesive function of electrodes and possible displacement.

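### If funded, section 23 pays only for completed treatment plus outcome data: the PTNS condition conflicts with the make-up rule, the TENS condition is unclear, and data alone earn nothing

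*Combined protocol and SAP*

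**What the plan says.** Section 23 (Compensation) opens with the current position: "At this time, no compensation will be provided to study participants". If money is found, each woman would receive $50 in two parts. The first is a "merchandise card when they complete 6 weeks of treatment (6 weekly sessions in the case of the PTNS group"; the second is "another \$25 merchandise card when they complete 12 weeks of treatment (12 weekly sessions in the case of the PTNS group". The section then says that the cards are "provided to patients when they complete 6 sessions or 12 sessions and the resulting outcomes measures, regardless of when they complete them", and its illustration begins "if a PTNS patient does 6 sessions of PTNS in an 8-week period": that woman gets her first card after week 8. The stated purpose is to offset the TENS device purchase and the inconvenience of the study, in particular the time taken by questionnaires. An IRB modification is planned to set the amounts.

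Section 12.1.1 (PTNS) lets a woman make up one missed session after week 12. Women who "miss more than one of their weekly office PTNS sessions, they will not be allowed to make up the extra sessions", and their participation or "outcome measurement will not be extended further than 13 weeks after randomization". The same section keeps them in the study and follows them for outcomes and adverse events. Section 13.2 analyses women as randomized whatever their compliance, unless they ask to be withdrawn or are withdrawn for safety or validity concerns.

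For TENS, section 12.1.2 prescribes daily use for 12 weeks. The threshold of 5 days per week appears in the compliance rules of section 12.1.2 and the per-protocol definition of section 13.3. Section 23 does not refer to it.

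**The concern.** The women whose primary outcome is hardest to obtain are those who have missed sessions or stopped. The intention-to-treat analysis needs their week-12 questionnaire, yet section 23 withholds the week-12 card from them even if they return everything. Section 13 names no method for missing outcomes, so any loss that differs by arm would pass straight into the non-inferiority comparison.

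Three further points add to this.

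- The condition is an exact count in one arm and open to interpretation in the other.
- Number of sessions completed is itself a study outcome, with a hypothesis in section 1.2.3 that compliance will be greater with TENS. A payment tied to sessions differently by arm bears on that comparison.
- Section 15 promises withdrawal without penalty. Losing a card on stopping treatment sits awkwardly beside that promise.

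**Working it through.** **The plan's own figures.** $25 + $25 = $50, which agrees with the $50 card in section 22. Section 5.3 needs 80 women and allows 30% dropout: 80 / (1 − 0.30) = 114.3, stated as 114, or 57 per arm.

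**Can a PTNS woman reach 12 sessions by week 13?** Sections 12 and 12.1.1 give 12 weekly slots and at most one make-up slot. With m sessions missed in weeks 1 to 12, the maximum is (12 − m) + 1 if a make-up is granted, and 12 − m if not.

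| Missed | Maximum with one make-up | Maximum with none |
|---|---|---|
| 0 | 12 | 12 |
| 1 | 12 | 11 |
| 2 | 11 | 10 |
| 3 | 10 | 9 |

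One miss is recoverable. Two are not, on either reading of the rule about extra sessions.

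**Section 23's own example.** Six sessions in 8 weeks leaves 13 − 8 = 5 weekly slots, so at most 6 + 5 = 11. This woman earns the first card and cannot earn the second within the study. Section 23's indifference to when sessions are completed therefore cannot operate beyond week 13 under section 12.1.1.

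**The TENS condition.** Daily use is 7 × 12 = 84 scheduled sessions; per-protocol status needs an average of 5 days per week, 5 × 12 = 60. Neither number is linked to payment. The sentence about 6 or 12 sessions is addressed to patients generally. Read literally for TENS, it would be met after 6 or 12 days, which does not fit a card due at 6 or 12 weeks.

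**How many PTNS women might be ineligible?** The documents give no attendance rate. Assume each session is attended independently with probability p and that every single miss is made up. Then P(two or more missed) = 1 − p^12 − 12(1 − p)p^11.

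- p = 0.95: 1 − 0.540 − 0.341 = 0.118 (unrounded terms), and 0.118 × 57 = 6.7, about 7 women.
- p = 0.90: 1 − 0.282 − 0.377 = 0.341, and 0.341 × 57 = 19.4, about 19 women.

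These count women who could not earn the second card. They do not predict missing questionnaires.

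**The case against.** The strongest reply is that the clause is dormant. The protocol is unfunded (Funding section), no payment is in force, and any payment needs a modification that could settle the wording. Sections 12.1.2 and 22 describe the planned card for both arms with no session condition. The stake is one $25 card, adverse effects are asked about weekly, and a 24-hour phone line is available (section 14). All of this is correct. It limits the urgency, but the planned modification is also the natural moment to correct the rule.

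Several stronger readings are tempting and are not supported.

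- *That payment is for sessions instead of data.* Section 23 requires the outcome measures too. The defect is that data without the sessions earn nothing.
- *That section 23 itself bars the second card after two misses.* The bar comes from section 12.1.1. Section 23 taken alone leaves the timing open, so the two sections conflict and must be reconciled.
- *That only PTNS women can lose a card.* A TENS woman who stops early has not completed 12 weeks of treatment either. The arms differ in how exactly the condition is defined; loss on stopping applies to both.
- *That 12% or 34% is a rate of missing outcomes, to be set against the 30% dropout allowance.* The percentages rest on assumed attendance and count ineligibility for a card in one arm. Section 12.1.1 keeps these women in follow-up. A like-for-like allowance would in any case be 30% of 57, about 17, and not the 34 across both arms.
- *That the primary comparison will be biased in a known direction.* The documents do not allow the size or the direction to be stated.

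**Conclusion.** The point holds as a cheap improvement, conditional on compensation being funded. As written, completed treatment is a necessary condition for each card. A PTNS woman with two missed sessions is limited to at most 11 within the study and loses $25 of the $50 even with complete week-12 data. The TENS condition cannot be applied without interpretation.

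The session limit follows from the documents by counting. The share of PTNS women affected, about 12% at 95% attendance and 34% at 90%, depends on assumed, independent attendance. The effect on missing data is a plausible risk that cannot be quantified. No sample size, power or alpha figure changes.

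**What to change.** In the modification that section 23 already plans, pay $25 on return of the week-6 outcome measures and $25 on return of the week-12 (or week-13) measures, in the same words for both arms and irrespective of sessions completed or treatment stopped. Delete the session-count wording and the 8-week example, so that section 23 no longer conflicts with the make-up rule and the 13-week limit in section 12.1.1. Carry the same wording into the consent form and into sections 12.1.2 and 22.

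This fits the stated purpose of the payment, since neither buying a device nor answering questionnaires depends on a session count. The cost is a wording change and a few extra $25 cards for women who miss sessions or stop treatment but give their data.

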## **24. Compensation for Research-Related Injury**

If participants are injured or become sick as a result of this study, which is extremely unlikely given the nature of the interventions, UNMHSC will provide emergency treatment at the study participant's cost. No commitment is made by the University of New Mexico Health Sciences Center to provide free medical care or money for injuries to participants of the study. Reimbursement for treatment for all related costs of care will be sought from the participant insurer, managed care plan, or other benefits program. The participant will be responsible for any associated co-payments or deductibles required by the insurance. Participants will be encouraged to report any illness or injury they believe to be related to the study to the investigator or research staff. Participants will be given telephone contact information for the Urogynecology office for the purpose of asking any questions or stating any concerns about the study or treatment as a research subject. They may also be directed toward the HRPO. This language will be stated in the consent document, and reviewed during the informed consent process.

## **25. Consent Process**

Patients will be approached about the research study at the Urogynecology clinic or via virtual consultation at UNM Eubank or SRMC during a discussion for the management of OAB/UUI. Each patient undergoes counseling in a private room with a closed door to ensure privacy. The physicians in the Urogynecology division and research staff will be able to give a paper or electronic consent to patients to allow for inclusion. REDCap will be utilized to eConsent participants with the HRRC approved PDF consent uploaded into REDCap. Our division routinely treats this condition and are highly qualified to counsel patients regarding the risks, benefits, alternatives for the treatment. Care will not be withheld if they decide not to participate. If the patient prefers, she may also be counseled about study participation via ZOOM or phone following her clinic appointment by providers or study personnel.

The patients who would like to participate in the study will be consented during their new or return visit in the Urogynecology clinic. Participants will have these multiple opportunities to ask any questions and they will also be provided with the clinic's contact information to get in touch with research investigators to address any additional questions or concerns.

PROTOCOL TITLE: INTENSE: INvestigation of TENS Efficacy versus Posterior Tibial Nerve Stimulation for overactive bladder

Subjects will be reassured that participation is completely voluntary and does not affect their treatment, their relationship with their providers, or the university to minimize the possibility of coercion or undue influence. The patients will be asked that they understand the opportunity to participate and their complete freedom to decline. This will also be asked if they understand and if they have any questions. There is no minimum time period needed between informing the patient of the study and time of consent. Subjects will be encouraged to take as much time as they need.

This study will obtain HIPAA authorization prior to enrollment. HIPAA authorization will be reviewed with all participants by the physician or research staff obtaining consent. Specific information that will be obtained includes prior medical history, surgical history, reproductive health history including child bearing, drug allergies, age, and ethnicity. This information will be obtained by health care providers, not research coordinators, as deemed necessary for a more complete and accurate medical history of the patient.

Subjects not fluent in English:

Patients will be consented with a certified translator if Spanish speaking. Spanish-speaking patients will be offered information about risks, benefits, and alternatives to study participation in a private setting and given adequate time to consider the risks and benefits of the study prior to offering consent or declining to participate. The Spanish consent will be translated from the English consent once the English consent is approved, and we will submit a modification in Huron IRB to update the study with Spanish materials in the future.

Cognitively Impaired Adults/Adults Unable to Consent/Use of a Legally Authorized Representative:

NA. Cognitively impaired subjects will not be included in this study.

Subjects who are not yet adults (infants, children, teenagers):

NA. Only subjects  $\geq 18$  years of age will be included in this study.

Waiver or Alteration of Consent Process (consent will not be obtained, required element of consent will not be included, or one or more required elements of consent will be altered)

NA. There will be no waiver or alteration of the consent process.

